[REDACTED] The surgery will be performed under local anaesthesia. Other anaesthetic options will be considered by the surgeon as appropriate for the subject. Then subjects will receive GT005 at one of the three doses ([REDACTED]) as a single administration in the form of a subretinal injection of 100 microlitres.

After surgery, subjects will remain in the clinic for up to 24 hours following the surgery to assess any acute issues resulting from the surgery. [REDACTED]

[REDACTED]

Subjects will undergo follow-up visits at Week 1, 5 and 8 post-dosing, every three months (at Weeks 12, 24, 36, and 48) for the first year, and at Weeks 72 (1.5 years), 96 (2 years), 144 (3 years), 192 (4 years), and 240 (5 years) post-dosing. At the Week 48 visit, subjects will be invited to consent to the additional follow-up (up to and including Week 240 visit). The Week 48 visit will be the time point used for the primary endpoint of the study. Week 240 (Year 5) will be the end of study visit.

Assessments carried out at the follow-up visits include ophthalmic examination, measurements of the size of GA, retinal examination, microperimetry, visual acuity (BCVA and LLVA) and [REDACTED] Blood samples will be taken for safety [REDACTED]

[REDACTED]

(as described in the Schedule of Assessments).

[REDACTED]

If a subject drops out or is withdrawn from the study, prior to the Week 48 visit, every reasonable effort will be made to complete the assessments scheduled for the Early Termination Visit.

If a subject does not agree to consent to long-term follow-up as part of this study, any ongoing AEs will be followed until resolution with subject consent.

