### 3. STATISTICAL METHODS

#### 3.1. General information

Two interim analyses and a clinical study report (CSR) are planned. First interim analysis will include data up to Week 72 from cohorts 1-4 with GT005 delivered via the transvitreal procedure. Second interim analysis will include data from cohorts 1-4 up to Week 96 and from Orbit SDS administration cohorts 5-7 up to Week 48. Clinical study report will be based on the analysis of all variables specified in this SAP from all 7 cohorts on data over 96 weeks.

All outputs will be incorporated into Word files and PDF files, sorted and labeled according to the International Conference on Harmonisation (ICH) recommendations, and formatted to the appropriate page size(s).

Tabulations will be produced for appropriate demographic, baseline, efficacy, biomarker assay, and safety parameters. For categorical variables, summary tabulations of the number and percentage within each category (with a category for missing data) of the parameter will be presented. For continuous variables, the number of observations, mean, median, quartiles, standard deviation, standard error (SE), minimum and maximum values will be presented. Where appropriate, 95% confidence intervals (CIs) for point estimates of the mean or proportion will be provided. Data will be listed and summarized using descriptive statistics by dose, by route of administration, and by assessment visits as appropriate. Efficacy and biomarker assay data will additionally be summarized by CFI rare variant and broad GA subgroups. All ocular evaluations and ocular adverse events, where appropriate, will be presented by eye (Study Eye, Fellow Eye).

No formal statistical hypothesis testing will be performed for this study.

Medical history, concurrent procedures and adverse events will be coded using the Medical Dictionary for Regulatory Activities (MedDRA). Prior and concomitant medications will be coded using World Health Organization (WHO) Drug Reference List dictionary version Mar 2020.

All statistical analyses will be performed using SAS statistical software (Version 9.4), unless otherwise noted.

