### 3.2. Missing data

There will be no imputation of missing data performed except for GA area growth analysis, which will be based on MMRM model and thus missing data will be implicitly imputed assuming Missing at Random (MAR). All data recorded on the CRF will be included in data listings that will accompany the clinical study report.

Missing adverse event (AE) dates are imputed as follows:

- If AE end year is missing, or AE is ongoing, the end date will not be imputed.
- If AE end month is missing, then AE end date = min(31 Dec of AE end year, date of study discontinuation/completion).
- If the AE end day is missing, then AE end date = min(Last day of the AE end month, date of study discontinuation/completion).
- If AE start year is missing and AE end date < TRT date, then AE start date = earliest visit date
- If AE start year is missing and AE end date => TRT date or ongoing, then AE start date = TRT date
- If both AE start and end dates are missing and AE is not ongoing, both dates are set to TRT date.
- If AE start year < TRT year or AE start year > TRT year, and
  - month is missing, then AE start date = 01 Jan of AE start year
  - day is missing, then AE start date = 01 of AE start month-year
- If AE start year = TRT year, and
  - month is missing and AE end date < TRT date, then AE start date = 01 Jan AE start year
  - month is missing and AE end date => TRT date or ongoing, then AE start date = TRT date
  - month < TRT month or month > TRT month, then AE start date = 01 of AE start month-year
  - month = TRT month, then AE start date = min(TRT date, AE end date)

The same algorithm will be applied to impute start and end of concomitant medication.

The imputed dates will only be used to classify events, medications, or procedures as treatment emergent, concomitant or concurrent. Imputed dates will only be used in the table analyses. Listings will display the available date data. Missing dates in medical history will not be imputed except the date of initial diagnosis of GA which will apply the same date imputation algorithm mentioned above.

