### 3.7. Efficacy analyses

Efficacy analyses will be conducted using the FAS by treatment dose and route of administration.

**GA area (mm^2)** change from baseline in the study eye as assessed by FAF will be presented in spaghetti plots and in a summary by visit table. It will also be summarized in a table and line plots as least-squares means with 95% CI by visit using MMRM model with fixed effects for treatment (defined as dose and route of administration), study visit, baseline GA area (mm^2), treatment by visit interaction and visit by baseline GA area interaction.

**Square root of GA area (mm)** change from baseline in the study eye will be presented in spaghetti plots and in a summary by visit table. It will also be summarized in a table and line plots as least-squares means with 95% CI by visit using MMRM model with fixed effects for treatment, study visit, square root of baseline GA area (mm), treatment by visit interaction and visit by square root of baseline GA area (mm) interaction. MMRM analysis will be repeated for CFI rare variant subgroups and [REDACTED] by replacing in the model treatment with subgroups of interest.

For MMRM analysis an unstructured covariance matrix will be used to model the within-patient error. If an MMRM model with an unstructured covariance matrix does not converge, a more restricted covariance matrix can be considered in the following order until convergence is reached: first-order autoregressive, Toeplitz, compound symmetry and variance components.

Additionally, scatter plots with linear trend lines for square root of GA area size (mm) change from baseline at the target analysis visit vs. last observed CFI levels before the target analysis visit in the vitreous and aqueous samples will be generated by treatment groups.

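### All four fallback covariance structures for the GA growth MMRM assume equal variance at every visit, so Week 96 intervals could be too narrow if the unstructured fit fails and the spread of GA change grows

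*SAP*

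**What the plan says.** SAP 3.7 models change from baseline in GA area (mm²) and in its square root (mm) with an MMRM. The fixed effects are treatment (dose and route), visit, baseline, and the interactions of treatment and baseline with visit. LS means with 95% intervals are tabulated and plotted by visit. "For MMRM analysis an unstructured covariance matrix will be used to model the within-patient error". For a fit that fails, the SAP gives this rule: "a more restricted covariance matrix can be considered in the following order until convergence is reached: first-order autoregressive, Toeplitz, compound symmetry and variance components".

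SAP 3.1 specifies SAS 9.4 and bases the clinical study report on data "from all 7 cohorts on data over 96 weeks". It also says: "No formal statistical hypothesis testing will be performed for this study".

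Two passages bear on how visible a poor fit would be. For square-root GA area, SAP 3.7 says that "change from baseline in the study eye will be presented in spaghetti plots and in a summary by visit table"; the paragraph on GA area in mm² plans the same displays. SAP 3.1 requires n, mean, SD and SE for continuous variables, and adds: "Where appropriate, 95% confidence intervals (CIs) for point estimates of the mean or proportion will be provided".

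**The concern.** In SAS, AR(1), Toeplitz, compound symmetry (CS) and variance components (VC) for the within-patient error each have a single variance for all visits; VC also sets the within-patient correlation to zero. A failed unstructured fit therefore goes straight from 28 covariance parameters to AR(1) with 2, and loses every visit-specific variance in that one step. No heterogeneous version is named, nor a robust standard error or a degrees-of-freedom method.

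The outcome is change from baseline in a progressive lesion. If patients' lesions grow at different rates, the spread of change widens with time. A common variance then averages small early variances with large late ones. The late intervals come out too narrow and the early ones too wide.

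GA change is a secondary endpoint and nothing is tested, so what is at stake is the precision reported in the LS-mean tables and plots. Week 96 is the last visit in the study-report analysis. Protocol 11.3.2 also plans to compare GA area with historical progression data.

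**Working it through.** The plan states no SD, interval width or power for this model (SAP 3.3: no sample size calculated), so there is no figure to reproduce. The check asks what each structure does under assumed truths.

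**Inputs from the documents.** FAF at Weeks 5, 12, 24, 36, 48, 72 and 96 (Protocol Tables 2 and 3), so 7 visits. About 65 subjects (Protocol 3.1). **Assumed:** five dose-by-route groups, and every SD below.

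**Covariance parameters at 7 visits.** Unstructured 7×8/2 = 28; Toeplitz 7; AR(1) 2; CS 2; VC 1; heterogeneous CS 8; heterogeneous AR(1) 8; heterogeneous Toeplitz 13.

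**Assumed truth.** A random slope plus measurement error shared through baseline: cov(i,j) = s²·tᵢ·tⱼ + e²·(1 + I[i=j]), with t = week/52 and s, e in mm.

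**Formula.** With complete data and both interactions with visit in the model, the LS mean at a visit does not depend on the covariance structure, and its model SE is proportional to the fitted SD at that visit. Let r = fitted SD / true SD. Coverage is P(|t₅₉| < 2.001·r), with 65 − 5 − 1 = 59 df. Each structure V was fitted to the true matrix S by minimising log|V| + tr(V⁻¹S).

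**Worked case (CS or VC, s = e = 0.10).** Variances at the seven visits are 0.0201, 0.0205, 0.0221, 0.0248, 0.0285, 0.0392 and 0.0541. The fitted common variance is their mean, 0.0299. So r = √(0.0299/0.0541) = 0.744, and Week 96 coverage is 85.8%.

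**Week 96 coverage (%) of a nominal 95% interval, complete data**

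| s, e | SD ratio, Week 96/Week 5 | AR(1) | Toeplitz | CS, VC | Het. CS | Het. Toeplitz | Het. AR(1) |
|---|---|---|---|---|---|---|---|
| 0, 0.10 | 1.00 | 95.0 | 95.0 | 95.0 | 95.0 | 95.0 | 95.0 |
| 0.05, 0.10 | 1.19 | 92.0 | 92.0 | 91.9 | 94.9 | 94.6 | 94.3 |
| 0.10, 0.10 | 1.64 | 86.6 | 87.0 | 85.8 | 94.7 | 93.3 | 92.9 |
| 0.15, 0.10 | 2.19 | 83.1 | 84.1 | 80.9 | 94.4 | 91.9 | 91.5 |
| 0.15, 0.05 | 3.96 | 81.1 | 84.6 | 74.8 | 94.1 | 88.7 | 89.1 |
| 0.20, 0.05 | 5.13 | 81.3 | 86.5 | 73.5 | 94.0 | 87.4 | 88.4 |

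Under AR(1), over the five growing-spread rows, the Week 96 interval is 89% to 66% of its correct width and the Week 5 interval 106% to 342%. Multiplying s and e by the same factor leaves r unchanged, so the table serves the mm and mm² analyses alike at equal SD ratio.

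**Other shapes.**
- Random walk plus the same error (SD ratio 1.1 to 3.0): AR(1) 93.7% to 83.7%, heterogeneous CS about 95%, heterogeneous AR(1) and Toeplitz 92.7% to 94.8%.
- Nearly exact straight lines (error SD 1%, 2% or 3% of the slope SD at Week 96): Toeplitz r = 1.13, 1.08 and 1.03, so coverage is 97%, 97% and 96%. AR(1) stays at about 82% and CS or VC at 71%.

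**Dropout.** A REML simulation (400 runs per scenario, 20% monotone dropout completely at random, assumed groups of 5/15/15/10/20, t with n − 6 df) gave Week 96 coverage, as the SD ratio rose from 1.2 to 5.1, of 93% to 77% for AR(1), 92% to 81% for Toeplitz, 92% to 70% for CS and about 94% for heterogeneous CS. VC was not simulated with dropout.

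**How likely is a failed fit?** Under monotone dropout the Week 96 regression has 5 groups + 1 baseline + 6 earlier visits = 12 coefficients, so an unstructured solution exists once 13 patients have Week 96 data. The binomial chance of fewer than 13 is 1.4×10⁻⁷ with 65 subjects and 50% dropout, and 0.021 with 30 subjects and 40% dropout. Existence is not the same as convergence in SAS, and neither that nor non-monotone gaps were simulated.

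**The case against.** The case against giving this much weight is strong. Two things must both happen: the unstructured fit fails and the spread grows. The documents show neither, and a solution very probably exists at the planned size. The SAP wording is permissive, so other structures are not forbidden. By-visit n, mean, SD and SE are already required for GA change on both scales. None of these depends on a covariance model, and a reader could compare them with the LS-mean intervals. The study is exploratory, and no decision rule rests on the Week 96 interval. The group sizes and dropout in the simulation are assumptions.

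All of that stands and fixes the weight as minor. It does not make the list sound, because a fallback is written for the case in which the first choice fails, and nothing requires the by-visit SE to be shown beside the LS mean.

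A reader might go further and infer any of the following, none of which the documents support:
- **The Week 96 intervals will be too narrow.** That needs both conditions, and Toeplitz escapes in the near-linear case.
- **28 parameters with about 65 subjects makes failure likely.** The existence figures point the other way.
- **The order of the list is the fault.** All four structures share the equal-variance assumption, so no reordering cures it.
- **False-positive claims are at risk.** No test is planned.

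**Conclusion.** The point holds as a minor weakness in a contingency rule. If the unstructured fit fails and the spread of GA change grows, AR(1), the first fallback, gives Week 96 coverage of about 92% at an SD ratio of 1.2 and about 81% at ratios of 4 to 5, and CS or VC falls to about 74%. Toeplitz lies between 92% and 84% over the same range, with the near-linear exception. If the spread is constant, all four give 95%.

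The sizes rest on assumed SDs and assumed growth shapes, since the documents give none. The direction for AR(1), CS and VC was the same in every growing-spread scenario tested. The fallback may never be used.

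**What to change.** Change the fallback sentence in SAP 3.7 so that structures with visit-specific variances come first:
1. heterogeneous compound symmetry (94–95% with complete data in the scenarios tested);
2. heterogeneous Toeplitz or heterogeneous AR(1) (about 87–95%, a partial repair under random slopes and close to nominal under a random walk);
3. the four homogeneous structures now named, only if these also fail.

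State in each MMRM output which structure was used.

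The cost is one SAP sentence, standard SAS covariance options and a footnote in the table shells. The downsides are 8 to 13 covariance parameters instead of 1 to 7, and wider late-visit intervals if spread does grow, which is then the more honest width. A separate ANCOVA at each visit is not needed; it would use only patients seen at that visit and give up the missing-at-random handling that SAP 3.2 relies on.

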## Statistical Analysis Plan

Sponsor:	Gyroscope Therapeutics		
Protocol:	GT005-01 (FOCUS)		
Document Version No.:	04.0	Document Date:	17-JUN-2024

The following **macular sensitivity parameters by Mesopic Microperimetry** will be summarized by visit:

- Fixation stability measured with bivariate contour ellipse area (BCEA) at 63% and 95% proportional values (Deg)
- Mean sensitivity (dB)
- Number of scotomatous points
- Percentage of fixation loss

## Statistical Analysis Plan

Sponsor:	Gyroscope Therapeutics		
Protocol:	GT005-01 (FOCUS)		
Document Version No.:	04.0	Document Date:	17-JUN-2024

**The rate of successful delivery of full dose GT005** to the subretinal space for patients treated using the Orbit Subretinal Delivery System (cohorts 5-7) will be reported as number of full doses delivered divided by number of Orbit SDS devices used. **Rate of successful balanced salt solution (BSS/BSS+)** delivered will be reported as number of BSS/BSS+ administrations divided by number of devices used. Additionally, percentage of patients with full dose of GT005 delivered among patients intended to be treated using SDS Orbit will be reported. Listing of failed deliveries of GT005 or balanced salt solution (BSS/BSS+) will be provided along with the reasons for delivery failures.

All efficacy endpoints will be provided in data listings for FAS.

### 3.8. Biomarkers and [REDACTED] analyses

Levels of complement factors in aqueous, vitreous and plasma samples will be graphically presented using geometric means and 95% CI over time (visit) by treatment administration route and, separately, by CFI subgroups (CFI rare variant and broad GA). Concentration values above upper limit of quantification (ULOQ) will be set ULOQ, values below lower limit of detection (LOD) will be set to LOD using **Table 4**.

[figure not shown]
Box plots of fold change from baseline for CFI levels at last sampling visit for the analysis period, separately for aqueous and vitreous samples, vs.:

- Treatment dose and route of administration
- CFI variant subgroup (CFI rare variant, Broad GA)

will be presented.

## Statistical Analysis Plan

Sponsor:	Gyroscope Therapeutics		
Protocol:	GT005-01 (FOCUS)		
Document Version No.:	04.0	Document Date:	17-JUN-2024

A summary of data outside of quantification limits by visit will be presented.

## Statistical Analysis Plan

Sponsor:	Gyroscope Therapeutics		
Protocol:	GT005-01 (FOCUS)		
Document Version No.:	04.0	Document Date:	17-JUN-2024

### 3.9. Safety Analyses

#### 3.9.1. Adverse events

Analyses of adverse events will be performed in the SAF for treatment-emergent adverse events (TEAE). TEAEs are adverse events that are first identified or worsened after receiving the study treatment. Only treatment-emergent adverse events will be presented in the summary tables. Adverse events will be coded using the MedDRA dictionary and presented by system organ class (SOC) and preferred term (PT). The number (and proportion) of patients with TEAEs will be summarized by treatment dose and administration route at each analysis timepoint according to Table 5. AEs occurred after surgery for treatment administration and before deferred GT005 administration will be listed and included in footnotes of relevant TEAE summary tables.

**Table 5** TEAE summaries by treatment dose per administration route (if applicable)

TEAE summary	AE categories		
	Ocular AE in the study eye	Ocular AE in the fellow eye	Non-ocular AE
All AEs by primary SOC and PT	Y	Y	Y
All AEs by maximum severity	Y	Y	Y
AEs related to study treatment by SOC and PT	Y		Y
AEs related to surgical procedure by SOC and PT	Y		Y
AEs related to Orbit SDS procedure by SOC and PT	Y		Y
SAEs by SOC and PT	Y	Y	Y
SAEs related to study treatment by SOC and PT	Y		Y
SAEs related to surgical procedure by SOC and PT	Y		Y
SAEs related to Orbit SDS procedure by SOC and PT	Y		Y

All adverse events occurring in the study will be listed in subject data listings. By-subject listings will also be provided for the following: subject deaths; serious adverse events;

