### 1.2. Study objectives and endpoints

Study objectives and related endpoints are described in Table 1 below.

[figure not shown]
**Table 1** Objectives and related endpoints

Objectives	Evaluation Criteria
Primary	
To evaluate the safety of GT005 at 3 doses	

Incidence of ocular and non-ocular treatment-emergent AEs (TEAEs) and treatment-emergent serious AEs (TESAEs) over 48 weeks

Secondary	
To evaluate the long-term safety of GT005 at 3 doses	

Incidence of ocular and non-ocular treatment-emergent AEs (TEAEs) and treatment-emergent serious AEs (TESAEs) up to 240 weeks

To evaluate the effect of GT005 on anatomical and functional visual outcomes	

Best corrected visual acuity (BCVA) and low luminance visual acuity (LLVA) score via the early treatment diabetic retinopathy study (ETDRS) chart up to 240 weeks

Macular sensitivity as assessed by Mesopic Micropertimetry up to 240 weeks

Change in GA area size as assessed by fundus autofluorescence (FAF) up to 240 weeks

To evaluate the performance of the Orbit SDS (US only)	

Rate of successful delivery of balanced salt solution (BSS) or BSS PLUS to the subretinal space

Rate of successful delivery of GT005 to the subretinal space

To evaluate the safety of the Orbit SDS (US only)	

Incidence of device-related AEs and SAEs

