## 2. SUBJECT POPULATIONS

### 2.1. Population definitions

The **All Enrolled Set** includes all patients who signed informed consent. This analysis set will be used to summarize patient disposition and for summaries of successful GT005 and BSS delivery rates of SDS orbit device.

The **Safety Analysis Set (SAF)** will include all subjects who have undergone surgery and received GT005. The SAF will be used for analysis of safety and laboratory data.

The **Full Analysis Set (FAS)** will include all subjects in SAF who have baseline and at least one post baseline value of GA area size via FAF in the study eye. The FAS will be used for analysis of efficacy data.

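### The Orbit device-AE incidence counts only TEAEs in GT005-dosed subjects, so device-related AEs in never-dosed subjects, or before a deferred dose, fall outside the rate

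*SAP*

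**What the plan says.** The secondary endpoint for the safety of the Orbit SDS is "Incidence of device-related AEs and SAEs" (SAP 1.2, Table 1; the same in protocol section 2). The GT005 safety endpoints in that table are limited to treatment-emergent events; this one is not. Protocol 9.4 makes any AE related to the Orbit cannulation procedure a device-related event, and protocol 9.1 treats a device-related serious injury as an SAE. Neither rule depends on GT005 having been given.

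The analysis rules are narrower:

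- SAP 3.9.1 fixes the set and the event type: "Analyses of adverse events will be performed in the SAF for treatment-emergent adverse events (TEAE").
- The SAF "will include all subjects who have undergone surgery and received GT005" (SAP 2.1). Protocol 11.2 assigns safety analysis to this set without an exception for the device.
- SAP 3.9.1: "TEAEs are adverse events that are first identified or worsened after receiving the study treatment", and "Only treatment-emergent adverse events will be presented in the summary tables". Protocol 11.3.4 also prescribes TEAEs for summaries by relationship to study medication or procedure.
- For deferred dosing, SAP 3.9.1 adds: "AEs occurred after surgery for treatment administration and before deferred GT005 administration will be listed and included in footnotes of relevant TEAE summary tables".
- Subjects who are not treated are classed as screen failures and may be replaced (protocol Synopsis, 4.1 and 4.4.1).

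Orbit performance is handled differently. The All Enrolled Set is used "for summaries of successful GT005 and BSS delivery rates of SDS orbit device" (SAP 2.1), and SAP 3.7 adds that the "percentage of patients with full dose of GT005 delivered among patients intended to be treated using SDS Orbit will be reported".

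**The concern.** The endpoint concerns the device, but entry to its numerator and denominator is governed by receipt of the drug. The protocol foresees that the two can separate during an operation. The Synopsis gives an AE during surgery as an example of why GT005 may be deferred, and protocol 9.5 includes a code for drug that was not administered among the actions taken for an AE. A device AE serious enough to stop the injection can therefore remove itself, or its subject, from the rate meant to measure it. That is selection on the outcome, and it tends to lower the rate.

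The contrast with performance sharpens the point. A failed Orbit delivery in a never-dosed patient counts in the performance summary of patients intended for Orbit treatment. The AE that caused the failure does not count in the safety incidence.

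**Working it through.** **Text check.** The Table 5 Orbit rows are applied to each kind of Orbit-related event:

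| Orbit-related AE | Subject in SAF? | TEAE? | In the Table 5 count? | Shown elsewhere |
|---|---|---|---|---|
| (a) Orbit surgery started, GT005 never given | No | No | No | AE listing; SAF exclusions counted and listed with reasons (SAP 3.4); failed-delivery listing if a delivery failed (SAP 3.7) |
| (b) Before a deferred dose, not worse afterwards | Yes | No | No | AE listing and table footnote |
| (c) During cannulation, before a same-day injection, not worse afterwards | Yes | No by the wording; possibly yes if derived by date | Open | AE listing |
| (d) After the injection | Yes | Yes | Yes | AE listing |

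Row (b) reads the footnote sentence as also covering AEs that begin during the abandoned operation. Row (c) is open because study day (SAP 3.1.1) and the date imputation used to classify emergence (SAP 3.2) work on dates, and no clock time appears. The SAP does not state whether emergence is derived by date or by time.

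**Size.** The documents give no expected device-AE rate and no number of undosed or deferred Orbit surgeries, so there is no figure to reproduce. The only input from the documents is the planned Orbit maximum, 5 + 5 + 20 = 30 (Cohorts 5 to 7). All event counts and probabilities below are assumptions. Confidence intervals are exact (Clopper-Pearson) 95%.

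Reference: 0/30 = 0%, upper limit 11.6%.

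Kind (a), *u* never-dosed subjects each with an Orbit AE; rate = (x + u)/(30 + u):
- From x = 0: 1/31 = 3.2% (0.1 to 16.7); 2/32 = 6.2% (0.8 to 20.8); 3/33 = 9.1% (1.9 to 24.3).
- From x = 3 (3/30 = 10.0%): 4/31 = 12.9%; 5/32 = 15.6%; 6/33 = 18.2%.

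Kind (b), and (c) if it is excluded, *d* dosed subjects each with an uncounted AE and no counted one; rate = (x + d)/30:
- From x = 0: 1/30 = 3.3% (0.1 to 17.2); 2/30 = 6.7% (0.8 to 22.1); 3/30 = 10.0% (2.1 to 26.5).

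Opposite direction, never-dosed subjects without an Orbit AE: from 3/30 = 10.0%, one gives 3/31 = 9.7% and three give 3/33 = 9.1%. In general, adding *u* undosed subjects of whom *y* had an AE raises the rate only if y/u exceeds x/30.

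Chance of at least one undosed subject among 30 started surgeries, 1 − (1 − p)^30: 26.0% for p = 0.01, 59.9% for p = 0.03, 78.5% for p = 0.05.

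**The case against.** The strongest reply is that the SAP does what the protocol tells it to do. Protocol 11.2 puts all safety data in the SAF, 11.3.4 prescribes TEAEs by relationship to procedure, and untreated subjects are screen failures by design. On this view the short endpoint label takes its population and event definition from those sections. This stands as an account of where the gap comes from: a reader might infer that the SAP departs from the protocol here, and it does not. It does not close the gap, because the endpoint names an incidence of device-related events without the limit placed on the GT005 endpoints beside it.

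Second, nothing is hidden. All AEs are listed, deferred-dose events are footnoted, and SAF exclusions and failed deliveries are reported with reasons. A reader might infer that these events vanish from the report; the documents say otherwise. But a listing or footnote adds nothing to a count or percentage, and the footnote does not reach never-dosed subjects. Extending it to them would improve visibility at little cost, but would leave the rate unchanged.

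Third, a reader might infer that every AE during cannulation is excluded, even in subjects dosed the same day. The documents do not settle this. If emergence is derived by date, such events may be counted.

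Fourth, the study is descriptive, no threshold is set for the device-AE rate, and the size rests on assumed counts. This stands, and it limits the severity.

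Fifth, a wider set brings in subjects without a post-dosing visit schedule. This is a real drawback, to be disclosed beside the result.

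**Conclusion.** The point holds for kinds (a) and (b) with high confidence: in the visible SAP, these events are outside the only incidence reported for the device-safety endpoint. For kind (c) confidence is low, because the derivation rule is not stated. Parts of the SAP are redacted, so the claim concerns the visible text only.

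The rate can be too low because an AE can itself prevent dosing. The documents do not show that it is too low. If no Orbit surgery ended undosed or deferred, and no uncounted AE occurred before an injection, the change is zero. With the planned maximum of 30 subjects, each omitted affected subject is worth about 3 percentage points, which is within the wide interval that any count from 30 subjects carries. Undosed subjects without an AE would move the rate down slightly.

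Severity is minor to moderate. The primary endpoint and the SAF/TEAE summaries of GT005 and general procedure safety are not in question.

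**What to change.** In SAP 2.1, define an Orbit Surgery Set: all subjects in whom Orbit SDS surgery was started, whether or not GT005 followed. In this set, report the incidence of device-related AEs and of device-related SAEs, overall for the Orbit route. Count Orbit-related events with onset or worsening from the start of the first Orbit surgery. Kind (c) is then counted however emergence is derived in Table 5.

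Keep every SAF/TEAE row of Table 5, including the two Orbit rows. Footnote the new tables with the number of never-dosed subjects and their shorter follow-up, since the protocol schedules visits from dosing. Record the analysis in SAP section 4, which now reports no changes, as an addition to protocol 11.2 and 11.3.4.

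The cost is one analysis set, two summary tables and one entry in section 4. No new data collection is needed, because protocol 9.1 captures AEs from consent. The downsides are a second denominator for device AEs, unequal follow-up within it, and possibly a slightly higher reported rate.
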